Subject level discontinuation will occur for any subject who develops a serious adverse event (SAE) due to infection confirmed to be caused by encapsulated organisms (see Section 8.3 for further information) or any subject with a sustained and significant reduction in renal function, as defined by one of the following: initiation of chronic dialysis, a confirmed and sustained eGFR ≤15 mL/min/1.73 m² or a confirmed and sustained reduction in eGFR of at least 30% which is drug related in the opinion of the PI. A reduction in eGFR would be considered confirmed if present on 2 separate consecutive measurements and considered sustained if the 2 measurements are at least 1 week apart. Subject level discontinuation can also occur for any individual for whom the PI deems it in the best interest of the patient to not continue in the study. Indication level discontinuation will occur if 2 or more subjects in a particular indication are discontinued by these criteria.

Subjects who do not meet the criteria for participation in the study (screen failure) may be rescreened. The timeframe and scope of eligibility reassessment will be determined by the sponsor. Any requests to rescreen an individual more than one time must be approved by the sponsor. For each rescreening, the individual must sign a new informed consent form and will be assigned a new identification number. Record of the subject's prior identification number and screening should be maintained with the source documents. Subjects who received vaccinations per protocol within 2 years of their rescreening date do not need to have the respective vaccination repeated but may do so at the discretion of the investigator.

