### 13.5. Treatment Discontinuation and Study Withdrawal

Subjects will be considered to have completed the study when they have completed the Week 72 exit visit activities described in the Schedule of Assessments in Section 4, when they have enrolled in a subsequent study of pegcetacoplan, or when they have discontinued study treatment and completed any early termination activities.

A subject may withdraw from the study at any time, for any reason, without prejudice to his/her future medical care by the physician or at the institution. If a subject discontinues or is withdrawn from study treatment for any reason, the study site must immediately notify the medical monitor.

Treatment may be discontinued and/or a subject's participation in the study may be discontinued, for any of the following reasons:

- 1. Any serious adverse event (SAE), clinically significant AE, severe laboratory abnormality, intercurrent illness, or other medical condition (including infections) that indicates to the PI that continued participation is not in the best interest of the subject.
- 2. Subject's decision to withdraw.
- 3. Subject's failure to comply with protocol requirements (including pregnancy) or study-related procedures.
- 4. Termination of the study by the sponsor, US Food and Drug Administration, or other regulatory authorities.
- 5. Liver Toxicity (please refer to Section 13.5.1 for further details).
- 6. Sustained and significant reduction in renal function (see more details below).

A sustained and significant reduction in renal function is defined by one of the following: initiation of chronic dialysis, a confirmed and sustained eGFR ≤15 mL/min/1.73 m² or a confirmed and sustained reduction in eGFR of at least 30% which is drug related in the opinion in the PI. A reduction in eGFR would be considered confirmed if present on 2 separate consecutive measurements and sustained if the 2 measurements are at least 1 week or apart.

The reason for treatment discontinuation and/or withdrawal from the study must be recorded in the subject's source document.

Subjects who discontinue study treatment prior to the end of the treatment period, should undergo all follow-up visits and procedures through study completion (Exit Visit), unless unwilling or unable, or consent has been withdrawn. Subjects who wish to fully withdraw from the study before Visit 15, should be encouraged to complete the Early Termination Exit Visit.

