#### 19. APPENDICES

# Appendix 1. Long-Term Extension Activities

## A1.1. Part B: Long-Term Extension Phase

This Appendix only contains information that is specific to the design and conduct of Part B, the Long-Term Extension Phase. Any processes, procedure, or information not described in this Appendix is identical to that described through the body of the main protocol.

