After completion of the 48-week treatment period, each subject will have the opportunity to enter Part B, the Long-Term Extension Phase, at the discretion of the investigator. If the subject does not enter Part B, he or she will enter a 24 week follow up period, consisting of 6 clinic visits at weeks 50, 52, 54, 60, 66, and 72 (Exit Visit). Various safety assessments will be undertaken during these clinic visits, and follow-up phone calls will be performed to gain relevant safety information. Patients will be maintained on their baseline treatment regimen during treatment and the follow-up period, as determined by the Principal Investigator (PI) in consultation with the medical monitor. During the study, changes to the baseline treatment regimen should be avoided to the extent possible and made only when required for the well-being of the patient, in the opinion of the PI.

Safety summaries will be presented over the screening period, 48 weeks of treatment and 24 weeks of follow-up, as well as the overall duration of the study.

An external, independent Safety Monitoring Committee (SMC) will assess the safety or tolerability data of the study.

Subject level discontinuation will occur for any subject who develops SAE due to infection confirmed to be caused by encapsulated organisms (see Protocol Section 8.3 for further information) or any subject with a sustained and significant reduction in renal function, as defined by one of the following: initiation of chronic dialysis, a confirmed and sustained eGFR \leq 15 mL/min/1.73 m2 or a confirmed and sustained reduction in eGFR of at least 30% which is drug-related in the opinion in the PI. A reduction in eGFR would be considered confirmed if present on two separate consecutive measurements and sustained if the two measurements are at least 1 week or apart. Subject level discontinuation can also occur for any individual for whom the PI deems it in the best interest of the patient to not continue in the study. Disease Group level discontinuation will occur if two or more subjects in a particular disease group are discontinued by these criteria.

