6.3. Analyses of Exploratory Endpoints

Changes and percentage of changes from Part A + B baseline and Part B baseline will be summarized by visits using both the ITT Population and PP Population for the following disease specific biomarkers:

- IgAN: autoantibodies to Gd-IgA1 and antiglycan antibodies
- LN: autoantibodies to dsDNA, C3 and C1q (listing only)
- C3G: C3 nephritic factor (C3NeF)

Additional disease parameters and/or biomarkers may also be analyzed.

Finally, the time to the composite clinical outcome will be summarized by disease group using Kaplan-Mier (KM) method. The detail of definition and search criteria is provided in the following table:

Composite clinical outcome category	Definition	Search criteria	
Doubling of serum creatinine	Doubling of the serum creatinine level from Part A baseline sustained for at least 30 days	Search post-baseline creatinine that is twice of Part A baseline, and the following assessment that is >=30 days away and is also twice of baseline; if 2nd assessment is missing but the subject discontinues treatment after 1 st doubling creatinine, this is also counted as an event. Any local lab can also be used for confirmation. Only assessments on or before treatment discontinuation will be used.	
Disease progression	Treatment discontinued due to disease progression	Search treatment discontinued reason due to disease progression	
Progression to chronic kidney disease stage 5	An estimated GFR of <15 ml per minute per 1.73 m2 confirmed by a second measurement after ≥30 days	Search for eGFR<15/min/1.73m2, and the following assessment that is >=30 days away and is also<15/min/1.73m2; if 2nd assessment is missing but the subject discontinues treatment then it is also counted as an event. Any local lab can also be used for confirmation. Only assessments on or before treatment discontinuation will be used.	
End-stage renal disease	Onset of end-stage kidney disease (defined as maintenance dialysis for ≥30 days)	Search concomitant procedure for dialysis and check (End Date-Start Date)>=30	
Kidney transplantation	Kidney transplantation	Search concomitant procedure for transplantation	
Death	Death from renal or cardiovascular causes	Search death with cause related to renal or cardiovascular	

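### In the SAP 6.3 composite, a Part B stop for a drug-attributed 30% eGFR fall is likely to be censored, while the same fall recorded as disease progression is an event

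*SAP*

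**What the plan says.** The composite is listed in SAP 2.1.1. SAP 6.3 defines it in a search table and summarises it by disease group with Kaplan-Meier. No censoring rule or date is given.

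- **Laboratory components.** Doubling of creatinine from the Part A baseline, and eGFR below 15, each need a second value at least 30 days later. A first qualifying value followed by discontinuation with no second value also counts. Both rows end with "Only assessments on or before treatment discontinuation will be used".
- **Disease progression.** Stopping for this reason is itself an event: "Search treatment discontinued reason due to disease progression". SAP 2.1.1 does not list this component, and Protocol 13.5 lists no such discontinuation reason.
- **Dialysis, transplantation, death.** These rows carry no cut at discontinuation.

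The renal stopping criteria in the Protocol synopsis include "a confirmed and sustained reduction in eGFR of at least 30% which is drug related in the opinion of the PI", where a reduction is "considered sustained if the 2 measurements are at least 1 week apart". SAP 3.1 repeats this: "a confirmed and sustained reduction in eGFR of at least 30% which is drug-related in the opinion in the PI". Appendix 1 carries main-protocol rules into Part B: "Any processes, procedure, or information not described in this Appendix is identical to that described through the body of the main protocol".

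The synopsis words the stop as mandatory ("Subject level discontinuation will occur for any subject who develops a serious adverse event (SAE", going on to the renal criteria). Protocol 13.5 words it as permissive: "Treatment may be discontinued and/or a subject's participation in the study may be discontinued, for any of the following reasons". Table A1 schedules chemistry and eGFR at the Early Termination Follow-up (ETF) and Early Termination Exit (ETE) visits, 6 and 12 weeks after treatment stops.

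**The concern.** A subject can be taken off drug for declining kidney function before reaching either laboratory threshold. From that moment the SAP ignores the creatinine and eGFR values that would show whether the decline went on. If the stop is attributed to the drug, no row of the table captures it. If the same stop is recorded as disease progression, it is an event.

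Censoring a subject because kidney function is falling is informative: that subject is more likely than the others to have a renal event soon. Here the censoring also depends on an investigator's causality opinion in an open-label study. Protocol 6.4 reports renal tubular degeneration in monkeys, of unknown significance in humans, and SAP 12 plans no safety monitoring committee for Part B. A curve that can turn on attribution is therefore a poor basis for a statement about freedom from renal events.

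**Working it through.** The documents give no event rate, precision or Part B group size for this composite, so there is no planned figure to reproduce. The check compares thresholds, then dates.

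**Inputs.** The SAP 6.2 equation has exponent -1.209 on creatinine above K (K = 0.7 mg/dL female, 0.9 male) and -0.329 (female) or -0.411 (male) below K. Entry eGFR is at least 30 (Protocol 11.1). Assumption: the 30% fall is measured from the same baseline as doubling. The protocol does not name its reference value.

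**Step 1: 30% fall against doubling, baseline at or above K.** Other terms cancel, so eGFR ratio = (creatinine ratio)^-1.209.
- Doubling: 2^-1.209 = 0.433, a fall of 56.7%.
- 30% fall: creatinine ratio = 0.7^(-1/1.209) = 1.34.
- Under steady decline, doubling comes at 0.567/0.30 = 1.9 times the time to the 30% mark (linear), or ln(0.433)/ln(0.7) = 2.3 times (exponential).

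**Step 2: 30% fall against eGFR below 15.**
- From 30: 0.7 x 30 = 21.0, while going below 15 needs a fall of more than 1 - 15/30 = 50%.
- From 60: 0.7 x 60 = 42.0, against a fall of more than 1 - 15/60 = 75%.

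So a subject stopped at the trigger has normally met neither laboratory component.

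**Step 3: where the ordering fails.**
- Female, baseline 0.40 mg/dL: doubling gives (0.80/0.7)^-1.209 / (0.40/0.7)^-0.329 = 0.851/1.202 = 0.708, a fall of 29.2%. Doubling and the trigger almost coincide.
- Male, baseline 0.45 mg/dL: 2^-0.411 = 0.752, a fall of 24.8%. Doubling comes first.
- Part B visits are 12 weeks apart. A decline of (56.7 - 30)/12 = 2.2 points of baseline per week passes from 30% to doubling between two visits. A first doubling recorded by the stop then counts, whatever the cause.

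**Step 4: dates.** Take a subject stopped at day 0 with creatinine at 1.34 times baseline, who is at twice baseline at ETF (day 42) and ETE (day 84). The two values are 42 days apart, which meets the 30-day confirmation. Both fall after discontinuation.

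| Recorded reason for stopping | Status under SAP 6.3 |
|---|---|
| Drug-related renal decline | No laboratory event; censored by Kaplan-Meier default unless dialysis, transplantation or qualifying death follows |
| Disease progression | Event |

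SAP 7.1 counts adverse events as treatment-emergent up to 56 days after the last dose. A day-42 visit falls inside that window, yet its creatinine cannot enter the composite.

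**Step 5: size.** With no earlier censoring, one reclassified subject moves cumulative incidence by 1/n: 1/6 = 16.7 points, 1/8 = 12.5, 1/12 = 8.3. The range 6 to 12 is the planned Part A group size. Only subjects who roll over enter this analysis, so Part B groups can be smaller.

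**The case against.** The strongest reply is that the gap is narrow and the harm is visible elsewhere. Much of this stands.

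- The cut applies only to creatinine and eGFR. Later dialysis, transplantation and renal or cardiovascular death are not barred.
- The other two renal stopping criteria, chronic dialysis and eGFR of 15 or less, closely match composite components. The gap is confined to stops between a 30% fall and the laboratory thresholds.
- A subject who has not doubled is correctly event-free for doubling. Counting a 30% stop as an event changes the endpoint, so it belongs in a sensitivity analysis.
- Only Part B stops matter. Subjects who stopped in Part A are outside the SAP 4.2 population, and those who roll over were judged to be benefiting.
- SAP 6.2 tabulates eGFR decreases of more than 25% by visit without regard to cause. SAP 7.1 tabulates drug-related events and events leading to discontinuation, SAP 7.2 gives chemistry shift tables, and Protocol 15.1.1 makes a laboratory change that leads to discontinuation an adverse event.
- The endpoint is exploratory, with no formal inference.

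A reader might infer that all drug-attributed decline is censored and all disease-attributed decline counted, or that the plan hides renal harm. The documents support neither. A first doubling or eGFR below 15 present at the stop counts under either attribution. Disease-attributed decline counts only if it is the recorded reason for stopping or another component is met. The safety tables report the decline.

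None of this corrects the curve: the discarded laboratory values and the unequal treatment of the two recorded reasons remain.

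**Conclusion.** The point holds in a limited form. For a Part B subject stopped for a drug-attributed eGFR fall of at least 30%, before doubling or eGFR below 15, the composite discards scheduled laboratory values that could show an event. It would probably censor that subject, where a stop recorded as disease progression would be an event. Each such subject shifts simple cumulative incidence by 1/n, at least 8.3 points in any group of 12 or fewer. The documents give no basis for estimating how many there will be.

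This rests on three conditions: baseline creatinine at or above K, or not far below it; the 30% fall taken from the same baseline as doubling; and default Kaplan-Meier censoring, which is inferred because the SAP states no rule. How the case report form codes reasons for stopping is not visible. No error rate, sample size or decision rule is affected. It is a cheap improvement to an exploratory endpoint and worth making.

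**What to change.** In SAP 6.3:

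1. Use creatinine and eGFR through the ETF and ETE visits for doubling and eGFR below 15, keeping the existing rule for a first qualifying value followed by discontinuation. Alternatively, show this as a sensitivity analysis beside the on-treatment curve.
2. Add one sensitivity curve in which any discontinuation for renal decline counts as an event whatever the attribution.
3. State the censoring rule and date, and print the number censored at discontinuation by reason beside the curve.
4. Reconcile the disease-progression row with SAP 2.1.1, which omits it. The mandatory stopping wording in the Protocol synopsis and the permissive wording in Protocol 13.5 must also be reconciled; this point takes no view on which should stand.

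The cost is SAP wording and a little programming, since the early-termination chemistry is already scheduled. Off-treatment values enter the analysis, so that curve no longer describes on-treatment experience alone. The event-free proportion may look slightly less favourable.

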#### 14.1.2. Prior and Concomitant Medications

To be eligible for entry into the study, subjects must be on a stable optimized treatment regimen for their disease, in the opinion of the PI, for at least 2 months prior to the first dose of pegcetacoplan (Visit 4), which may include, but is not limited to, use of immunosuppressive agents, antihypertensives and/or antiproteinurics.

All other prior medications administered within 12 Weeks of Screening Visit 3a will be collected.

Use of rituximab, belimumab, and eculizumab during the study (and/or within 6 months prior to the first dose of pegcetacoplan) must be discussed with the sponsor for consideration and approval.

All medications and procedures administered to subjects from the time of informed consent through the End of Study Visit are regarded as concomitant and will be documented.

To the extent possible, baseline treatment regimens (including medications, dietary restrictions, and lifestyle modifications), should not be changed during the study, except as necessary for the well-being of the patient, in the opinion of the PI.

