2.1.1. Efficacy Endpoints

- Proteinuria reduction over time based on urinary protein to creatinine ratio (uPCR)
- Change and % change from baseline in disease specific biomarkers over time:
 - Complement biomarkers (Serum C3, C3a, C4, C5a, AH50 and CH50, Plasma sC5b-9)
 - Serum albumin levels
- Complete clinical remission: defined as normalization of proteinuria as defined by <200 mg/g uPCR over time
- Stabilization or improvement in eGFR over time: defined as no more than a 25% decrease relative to baseline
- Changes and percentage changes from baseline in eGFR over time
- Time to the composite clinical outcome (first occurrence of any of the following: sustained doubling of serum creatinine, chronic kidney disease [CKD] stage 5, end-stage renal disease [ESRD], Kidney transplantation, or death from renal or cardiovascular causes)

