13.6.2. Missing Dates Information for Prior or Concomitant Medications

For the purposes of determining prior and concomitant medications, if a partial date is recorded, the following convention will be used to assign the medication dates:

- If a start date is missing the day information and month/year is the same as first dose date then use first dose date, else '01' will be used for the day; if a start date is missing the month and the year is the same as first dose date then use first dose date, else January will be used for the start month.
- If a stop date is missing the day information and month/year is same as last study date then use last study date, else last day of the given month will be used for the stop day; if a stop date is missing the month and year is the same as last study date then use last study date, else December will be used for the stop month.

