13.6.3. Missing Date Information for Adverse Events

For AEs with partial start dates, non-missing date parts will be used to determine if the AE is treatment-emergent or not. If a determination cannot be made using the non-missing date parts as to when the AE occurred relative to study drug administration, e.g. AE start year and month are the same as the year and month of the first dose of investigational product, then the AE will be classified as treatment-emergent.

To facilitate categorization of AEs as treatment emergent, imputation of dates can be used. For AEs, the default is to only impute incomplete (i.e., partially missing) start dates. Incomplete stop dates may also be imputed when calculation of the duration of an AE is required per the protocol. If imputation of an incomplete stop date is required, and both the start date and the stop date are incomplete for a subject, impute the start date first.

- Rules to impute incomplete start date are the same as stated in Section 13.6.2.1.
- Rules to impute incomplete stop date are the same as stated in Section 13.6.2.2.

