15.2. Changes from Analyses Specified in the Previous Version of the SAP

Statistical Analysis Plan Version 1.0 was used to produce results for the Part A (Core Study Phase). This SAP is used to present the safety and efficacy results for Part B (Long-Term Extension Phase). Since there were no specified objectives and endpoints defined in the protocol for Part B, modified endpoints from the Part A are used for Part B analysis.

Statistical Analysis Plan 2.0 Protocol Number: APL2-201

16. **REFERENCES**

Not applicable.

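### The composite renal outcome has five events in SAP 2.1.1 but six in the SAP 6.3 table, and the table's ESRD search cannot count dialysis recorded as ongoing without an end date

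*SAP*

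**What the plan says.** SAP 2.1.1 lists the time to a composite clinical outcome among the efficacy endpoints. The outcome is the first occurrence of "sustained doubling of serum creatinine, chronic kidney disease [CKD] stage 5, end-stage renal disease [ESRD], Kidney transplantation, or death from renal or cardiovascular causes".

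SAP 6.3 summarises this outcome by disease group with the Kaplan-Meier method and refers to a table for the detailed definitions and search criteria. Besides the five events above, the table has a category called disease progression, defined as "Treatment discontinued due to disease progression". Its search looks only at the recorded reason for stopping treatment.

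The end-stage renal disease (ESRD) row defines the event as maintenance dialysis lasting 30 days or more. Its search instruction is "Search concomitant procedure for dialysis and check (End Date-Start Date)>=30".

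Protocol 14.1.2 sets the period for which procedures are documented: "All medications and procedures administered to subjects from the time of informed consent through the End of Study Visit are regarded as concomitant". The SAP's rules for incomplete dates are in two places. Section 13.6.2 opens "For the purposes of determining prior and concomitant medications, if a partial date is recorded", and section 13.6.3 opens "For AEs with partial start dates, non-missing date parts will be used to determine if the AE is treatment-emergent or not".

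On changes, SAP 15.1 reports none from the protocol. SAP 15.2 says that the protocol set no Part B endpoints and that "modified endpoints from the Part A are used for Part B analysis".

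**The concern.** One endpoint has two definitions in the same SAP. A programmer working from 2.1.1 and one working from 6.3 could produce different curves. The difference is not a matter of search detail: the extra row has its own category, definition and search. The creatinine, CKD stage 5 and ESRD rows carry thresholds and 30-day criteria, whereas this row needs only a recorded reason.

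In the ESRD row, the definition and the search beside it disagree about dialysis that has not ended. The definition does not require dialysis to have stopped, but the search needs an end date. Followed literally, it counts dialysis that ended after 30 days and can miss dialysis that never ended.

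The two faults act in opposite directions. The first can add events that are not in the stated endpoint. The second can omit an event that meets the SAP's own definition, or date it late if another row catches the subject afterwards.

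**Working it through.** The SAP gives no event count or power figure for this endpoint, so there is no planned number to reproduce. The check compares the two lists and then applies the search rule to test records.

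**1. Component lists**

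| Event | SAP 2.1.1 | SAP 6.3 table |
|---|---|---|
| Doubling of serum creatinine | yes | yes |
| CKD stage 5 | yes | yes |
| ESRD | yes | yes |
| Kidney transplantation | yes | yes |
| Renal or cardiovascular death | yes | yes |
| Treatment stopped for disease progression | no | yes |
| Total | 5 | 6 |

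The lists differ by exactly one event, and nothing in 2.1.1 is missing from 6.3. The protocol's endpoint lists (9.2.1 to 9.2.3) contain no such composite, so they cannot settle which list is meant.

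**2. The ESRD rule on test records** (invented durations; rule: end minus start at least 30 days)

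| Dialysis record | End minus start | Counted by the search? | Meets the definition? |
|---|---|---|---|
| Ended after 29 days | 29 | no | no |
| Ended after 30 days | 30 | yes | yes |
| Ended after 90 days | 90 | yes | yes |
| Ongoing at 300 days, no end date | missing | no | yes |

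A missing difference does not satisfy the 30-day condition. SAP 13.6.2 covers medications with partial dates, and 13.6.3 applies the same rules to adverse events. Neither covers a procedure or a wholly absent end date.

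**3. Would the dialysis be known to the study?** Protocol Table A1, note a, schedules an early termination follow-up visit 6 weeks after treatment stops and an exit visit 6 weeks later. Suppose dialysis starts on the day the drug stops and continues:

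- follow-up visit: 6 × 7 = 42 days of dialysis
- exit visit: (6 + 6) × 7 = 84 days of dialysis

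Both exceed 30, so the definition is met within observed follow-up.

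**4. Would another row catch the subject?** There are five other rows: creatinine doubling, CKD stage 5, disease progression, transplantation and death.

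- The creatinine and CKD 5 rows accept a single qualifying value if the subject then discontinues, but only values on or before discontinuation count. Starting chronic dialysis is itself one of the discontinuation criteria (Protocol 13.5, SAP 3.1), which can close that window.
- From Week 60 onward, visits with chemistry are 12 × 7 = 84 days apart with windows of ±7 days. The longest in-window gap is 84 + 7 + 7 = 98 days if no unscheduled sample is taken. A decline and a dialysis start inside that gap can leave no qualifying on-treatment value.
- Transplantation and death have no on-treatment limit, but may never occur or may occur much later.

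**5. Size of one misclassification.** The plan is 6 to 12 patients per disease in Part A; Part B numbers are not given. One subject is 1/6 = 16.7 or 1/12 = 8.3 percentage points of a crude event proportion, and more in a smaller rollover group.

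**The case against.** The best case on the other side has five parts.

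*The programmed analysis is clear.* SAP 6.3 says its table holds the detailed definitions, so the table would be followed and 2.1.1 was simply not aligned. That is a plausible history, but the report would still carry an endpoint whose stated definition differs from what was counted. SAP 15.1 and 15.2 record changes from the protocol and from SAP 1.0, which is not available here. Their silence on the mismatch therefore proves little either way.

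*Disease progression may never be recorded.* A reader might infer from Protocol 13.5, whose six discontinuation reasons do not include it by name, that the row is empty or invalid. The documents do not support that. The list gives grounds for stopping, not form categories, and both its broad medical reason and its renal-function reason could cover progression.

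*The eCRF is not visible.* An ongoing procedure might be closed with a visit date, or a programmer might impute one. This stands as a condition on the second half of the point. The SAP itself states no such rule.

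*Most dialysis subjects would enter by another row.* This has force, especially for creatinine doubling. With the exponent in SAP 6.2, creatinine above K and age held fixed, doubling multiplies eGFR by 2^(−1.209) = 0.433. For any baseline eGFR above 15/0.433, about 35, doubling is therefore reached before eGFR falls below 15. Entry requires only eGFR of 30 or more, so for most of the eligible range the creatinine row triggers first. It has the same on-treatment limit, so the gap narrows but does not close.

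*The sampling gap is not uniform.* A reader might apply 98 days to all of Part B. Subjects who change regimen at Part B entry have chemistry at weeks 1, 2 and 4. Week 48 has a ±2-day window, so Week 48 to Week 60 is at most 84 + 2 + 7 = 93 days. Unscheduled tests are also allowed.

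**Conclusion.** Both halves hold. SAP 2.1.1 and 6.3 define different composites, five events against six, and the Kaplan-Meier summary can count events outside the 2.1.1 definition. This needs no assumption beyond the text. The ESRD row cannot count ongoing dialysis if it is recorded without an end date; that half depends on a form that is not shown.

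A reader might infer more. The documents do not support saying that the composite as a whole misses dialysis patients, since five other rows may catch them. Nor do they support a wrong test result: SAP 6 applies no inferential statistics and summarises efficacy for C3G and IgAN only. The on-treatment limit in the creatinine and CKD 5 rows is an explicit choice in the SAP and is not counted here as an error.

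The consequence is possible misclassification of individual subjects in small-group descriptive curves. The number affected cannot be determined from the documents and may be zero. Correction is still worthwhile, because the contradictions are plain and cheap to remove.

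**What to change.** 1. Use one component list in SAP 2.1.1 and 6.3. If it has five events, delete the disease-progression row and report stops for that reason separately. If it has six, add the event to 2.1.1 and state how it is identified.
2. In the ESRD row, state that for dialysis recorded as ongoing, the end date in the 30-day check is the last date on which the subject was known to be on dialysis (last contact). The data cut-off date should not be used: a subject lost after 10 days of dialysis could then pass the check without 30 observed days. With last contact, the test record ongoing at 300 days becomes an event if the subject was seen on dialysis that day, and the three ended records keep their results.
3. State that the dialysis start date is the event date.
4. Make the changes together, because deleting the disease-progression row also removes one route by which a dialysis case might be counted.

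The cost is SAP wording, minor programming and a check of how the eCRF records ongoing procedures. No new data collection is needed.
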